10.4.6. Response Review

Radiology assessments for DF/HCC sites will be provided by the DF/HCC tumormetrics core. Assessment for other participating sites should be performed per local protocols. All complete or partial responses in patients with measurable disease should be confirmed by the DF/HCC tumormetrics core. Please see Appendix H for procedures for submission of materials for DF/HCC tumormetrics review from non-DF/HCC participating institutions.

10.5. Other Response Parameters

Criteria for CA-125 response can be found in Section 10.2.

11. ADVERSE EVENT REPORTING REQUIREMENTS

11.1. General

Adverse event collection and reporting is a routine part of every clinical trial. This study will use the descriptions and grading scales found in the revised NCI Common Terminology Criteria for Adverse Events (CTCAE) version 4.0 will be utilized until March 31, 2018 for AE reporting. CTCAE version 5.0 will be utilized for AE reporting beginning April 1, 2018. All appropriate treatment areas should have access to a copy of the CTCAE version 5.0. A copy of the CTCAE version 5.0 can be downloaded from the CTEP web site http://ctep.cancer.gov/protocolDevelopment/electronic_applications/ctc.htm.

Information on all adverse events, whether reported by the participant, directly observed, or detected by physical examination, laboratory test or other means, will be collected, recorded, followed and reported as described in the following sections.

Adverse events experienced by participants will be collected and reported from initiation of study medication, throughout the study, and within 30 days of the last dose of study medication. Participants who experience an ongoing adverse event or related to a study procedures and/or study medication beyond 30 days will continue to be contacted by a member of the study team until the event is resolved, stabilized, or determined to be irreversible by the participating investigator.

Participants should be instructed to report any serious post-study event(s) that might reasonably be related to participation in this study. The investigator should notify the IRB and any other applicable regulatory agency of any unanticipated death or adverse event occurring after a participant has discontinued or terminated study participation that may reasonably be related to the study.

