5.1.4. Pre-Cycle 1 Therapy: Translational Component

- All patients will be *strongly* encouraged to participate in the translational component of the trial. Travel to and from the NCI and all costs of imaging, blood draws, biopsy, or fluid sampling done at the NCI will be provided in kind. A stipend to assist with cost of the local stay during this aspect of the trial will be provided, or the patient can elect hospital admission at no cost.
- Biopsiability will be determined prior to scheduling the NCI visit using most recent tumor imaging. This will be followed by an on-study chest/abdominal/pelvic CT with oral and IV contrast obtained the day of evaluation at NCI. A copy of this scan will be provided to the home institution for use in subsequent tumor measurements.
- Patients will be seen at NCI with a copy of their signed protocol consent from their home institution.
- Drug therapy will be initiated after acquisition of initial translational components and dispensed for the 28-day cycle.
- Translational component sample acquisition will occur:
 - Prior to starting therapy
 - Prior to day 3: 2-8 hours after the 5th dose of olaparib (d1 will start with the am dose) and the 3rd dose of cediranib (the first dose of cediranib will be administered at the same time as the first dose of olaparib).

Process	Pre-treatment	Day 3
Blood for PBMCs, DNA, and CECs	X	X
Plasma and serum for cytokines	X	X
DCE-MRI imaging	X	X
Biopsy: core of tumor, involved skin, or malignant effusion sampling	X	X

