6. EXPECTED TOXICITIES AND DOSING DELAYS/DOSE MODIFICATIONS

Dose delays and modifications will be made using the following recommendations. Toxicity assessments will be done using NCI Common Terminology Criteria for Adverse Events (CTCAE v5.0). CTCAE v 5.0 is identified and located on the CTEP website at (http://ctep.cancer.gov/protocolDevelopment/electronic_applications/ctc.htm).

If possible, symptoms should be managed symptomatically. In the case of toxicity, appropriate medical treatment should be used (including anti-emetics, anti-diarrheals, etc.).

All adverse events experienced by participants will be collected from the time of the first dose of study treatment, through the study and until the final study visit. Participants continuing to experience toxicity at the off study visit may be contacted for additional assessments until the toxicity has resolved or is deemed irreversible.

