8.13. Post-progression Tissue Analysis

At the time of progression, where possible, core needle biopsies from a new lesion or site of progression will be obtained. The biopsy will be taken at the time of drug discontinuation or within the 30d follow up period pending patient consent. This research biopsy will be optional and performed only if there is minimal risk. In BRCA mutation carriers, research sequencing of BRCA will be performed from the tissue to test for the presence of secondary mutations that can restore BRCA function, as well as the presence of other proteins (e.g. 53BP1), identified as potentially mediating PARP-inhibitor resistance. Pending tissue availability, other markers of DNA repair and vascular endpoints such (e.g. RAD51, γ H2AX, VEGFR, CD31) will also be examined.

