- j: ECG done prior to Cycle 1 and 2, and then prior to every cycle if clinically indicated. The pre-study ECG may be used as the Cycle 1 ECG if performed within 7 days of Cycle 1 Day 1.
- k: MUGA or echocardiogram should be done at baseline and every 4 cycles for those patients at increased risk for compromised LVEF. Increased risk patients have had one or more of the following: (1) prior treatment with anthracyclines, (2) prior treatment with trastuzumab, (3) NY Heart Association classification of II, (4) prior central thoracic RT, (5) history of myocardial infarction within the 12 months prior.
- l: beta-HCG for women of childbearing potential.
- m: Tumor measurements by CT scans or MRI will be performed within the 4 weeks prior to starting cediranib/olaparib and will be performed after every 8 weeks (+/- 1 week) of treatment. If a partial or complete response is noted, a confirmatory CT scan or MRI should be performed. The next planned restaging CT scan or MRI may be used as the confirmatory scan. For patients in the Phase 2 portion of the trial, the frequency of restaging studies will decrease to once every 12 weeks (+/- 1 week) after the 20th cycle of treatment.
- n: The Family Risk Assessment questionnaire (Appendix I) should be completed by the patient and returned to the study staff by Cycle 2.
- o: For patients opting to participate in translational studies at the NCI. Study schedules will be as per Section 5.1.4.
- p: Off-treatment assessments should be performed within 30 days of stopping study treatment.
- q: For patients in the Phase 2 portion of the trial who have been on trial for greater than 4 years without evidence of disease progression, the treating investigator may choose to decrease the frequency of re-staging CT scans to once every 4 cycles.
- r: For patients in the Phase 2 portion of the trial who have been on trial for greater than 4 years without evidence of disease progression, the treating investigator may choose to decrease the frequency of visits to once every 2 cycles. These patients should have CBC with differential, serum chemistry, and urine protein assessment (UPC or urinalysis) performed and con-meds, adverse events, and blood pressure diary should be reviewed in-person or by telephone with the study team, but all other assessments may be omitted.

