11.2. Definitions

11.2.1. Adverse Event (AE)

An adverse event is any undesirable sign, symptom or medical condition or experience that develops or worsens in severity after starting the first dose of study treatment or any procedure specified in the protocol, even if the event is not considered to be related to the study.

Abnormal laboratory values or diagnostic test results constitute adverse events only if they induce clinical signs or symptoms or require treatment or further diagnostic tests.

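### Adverse event collection starts at the first dose although the definition starts at any protocol procedure, leaving pre-dose research sampling without a clear collection rule, and the end of the window is stated in two ways

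*Combined protocol and SAP*

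**What the plan says.** **Start of collection.** Section 11.1: "Adverse events experienced by participants will be collected and reported from initiation of study medication". Section 6 says that events "will be collected from the time of the first dose of study treatment, through the study and until the final study visit". The definition in Section 11.2.1 is wider: an event counts if it develops or worsens "after starting the first dose of study treatment or any procedure specified in the protocol".

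**Procedures before the first dose.** The table in Section 5.1.4 lists blood sampling, DCE-MRI, and biopsy (tumor core or involved skin) or effusion sampling, once pre-treatment and once on day 3. On the order of events it says: "Drug therapy will be initiated after acquisition of initial translational components". Section 8.3 asks for at least two 18-gauge cores.

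**End of collection.** The full rule in Section 11.1 is that events are "collected and reported from initiation of study medication, throughout the study, and within 30 days of the last dose of study medication". Appendix G 5.10.5 also uses 30 days after the last dose. Section 6 stops at the last visit instead. Footnote p of the Phase II calendar (Section 9.2) sets that visit loosely: "Off-treatment assessments should be performed within 30 days of stopping study treatment". The Phase I and I-T calendar (Section 9.1) gives no timing for it.

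**Research biopsy after progression.** Section 8.13: "The biopsy will be taken at the time of drug discontinuation or within the 30d follow up period pending patient consent".

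**The concern.** A complication of the baseline research biopsy meets the plan's definition of an adverse event, yet it occurs before the date on which two sections say collection opens. A site that follows Sections 6 and 11.1 to the letter can properly leave it off the form. The procedure is done for research, and Section 5.1.4 strongly encourages patients to take part, so its harms should be on the record. The case least protected is the patient whose complication prevents treatment from starting.

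At the other end, two rules give different closing dates. Neither calendar schedules an adverse event contact after the off-treatment visit, and the next routine contact in Section 5.6 is the six-monthly check of vital status. How actively new events are sought in the first month after treatment then depends on when a site books the visit and which section it follows. At stake is the completeness of the safety record, not the efficacy analysis.

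**Working it through.** No figure in the plan has to be reproduced here. The check sets the rules side by side and traces events through them.

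**1. When each rule opens**
- Sections 6 and 11.1: first dose.
- Appendix G 5.10.5 (the adverse event form): while on treatment. Section 12.1.2 ties submission of that form to the end of a cycle.
- Sections 10.1.1 and 14.3.1: evaluable for toxicity from first treatment.
- Section 11.2.1: first dose or any protocol procedure.
- Section 11.3: information taken at each contact, with no start date.
- Section 9.2: no adverse event assessment marked in the pre-study column.

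**2. Which scheduled sampling falls outside**

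Section 5.1.4 schedules two samplings. The day 3 sampling follows the fifth olaparib dose and is inside the window. The pre-treatment one is outside it: 2 − 1 = 1 of 2.

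**3. Tracing an event that starts after baseline sampling and before the first dose**
- *Resolves before dosing, no hospitalization:* an adverse event under 11.2.1, but outside Sections 6, 11.1 and Appendix G 5.10.5. Not clearly required.
- *Worsens after dosing:* worsening is part of the 11.2.1 definition and falls inside the window. Collected.
- *Grade 3 to 5 with hospitalization:* a bullet in Section 11.5.1 requires a report whatever the attribution, with no start date, although it sits in guidance on investigational agents. Probably caught.
- *Prevents the first dose:* the window never opens, the patient is not evaluable for toxicity under 10.1.1, and Section 4.1 allows the registration to be canceled. Not clearly required unless the Section 11.5.1 bullet applies.

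The length of the interval is not given. Section 4.1 asks for treatment within 5 days of registration, but the documents do not say whether sampling comes before or after registration, so this does not bound it.

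**4. The end of the window**

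Let *v* be the day of the Phase II off-treatment visit, from 0 to 30. Assume that the last visit in Section 6 means this visit, and that the stopping day is the day of the last dose. Section 6 then gives *v* days of collection, while 11.1 and Appendix G 5.10.5 give 30. The difference is 30 − *v*:
- *v* = 30: 30 − 30 = 0 days
- *v* = 14: 30 − 14 = 16 days
- *v* = 0: 30 − 0 = 30 days

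**5. Biopsy after progression**

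The window is tied to the last dose and not to the procedure. On the same assumption, a biopsy on day *b* leaves 30 − *b* days for a new event to fall inside it. For a biopsy on day 28 this is 30 − 28 = 2 days. An event that has begun by then and is still ongoing is followed further under 11.1.

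**The case against.** The strongest reply is that the plan catches more than Sections 6 and 11.1 suggest. Section 11.3 has all adverse events recorded, with information taken at each contact. The calendar's column for assessments before each cycle includes an adverse event check, so a contact just before Cycle 1 is arguably scheduled. Section 11.5.1 covers hospitalized grade 3 to 5 events, and Section 11.1 itself mentions events related to study procedures. This stands far enough that a reader who infers that biopsy harms are never collected goes too far. It does not close the gap. Section 11.3 sets no start date, two other sections do, and what is learned at a contact before Cycle 1 still precedes the stated window.

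On the end date, Section 11.1, Appendix G 5.10.5 and the expedited reporting tables all use 30 days, and Section 6 does not define its last visit as the off-treatment visit. Ongoing events are followed past day 30, participants are told to report serious later events, and attributable severe events after day 30 still need expedited reports. This also stands. A reader might infer that collection stops at an early visit, but the documents show only an inconsistency. What remains is that no scheduled contact supports the 30-day rule after an early visit. The later reporting rule also depends on attribution, which Section 11.2.4 defines in relation to study treatment, so it does not clearly reach a pure biopsy complication.

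A reader might further infer that the arms are affected unequally. Footnote p applies to both arms, and nothing in the documents shows different visit timing. Drug toxicity is counted from first treatment by design, so a pre-dose biopsy event would not enter that comparison.

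Finally, the change may come late for baseline sampling: Phase II accrual was planned over 18 months, and this version already provides for Phase II patients on trial for more than 4 years. That is a fair inference, but the documents do not say whether baseline sampling is finished. The end-of-window point still applies to anyone on treatment.

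**Conclusion.** The concern holds in a limited form. The start dates in Sections 6 and 11.1 contradict the definition in 11.2.1, and the contradiction has content because invasive research sampling precedes the first dose. The exposed events are those that arise between baseline sampling and the first dose, do not worsen after dosing and do not fall under the hospitalization bullet. Among them are events in patients who never start drug.

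The two end dates can differ by 0 to 30 days in Phase II, on the assumptions in step 4 of the working. They need reconciling; they do not establish that collection ends early.

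The number of missed harms cannot be estimated. The documents give neither a participation rate for the translational component nor a complication rate. Multiplying the 90 Phase II patients by an assumed participation rate would count procedures, not lost events. PFS, sample size, power and alpha are unaffected.

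**What to change.** In Sections 6 and 11.1 and Appendix G 5.10.5, state one window:
- It opens at the first protocol-specified research procedure, at least for procedure-related events and serious adverse events, and includes patients who never start drug.
- It closes 30 days after the last dose.
- Procedure-related events are also collected after any post-progression research biopsy, for a period the protocol should state.
- Procedure-related events are reported separately. Drug toxicity continues to be counted from the first dose, so Sections 10.1.1 and 14.3.1 need no change.

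In Sections 9.1 and 9.2, add a telephone adverse event check at about day 30 for patients whose off-treatment visit is earlier. If baseline sampling is already complete, events between sampling and first dose can be sought from source records.

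The cost is amendment wording, a few more adverse event forms and one telephone call for some patients. No treatment rule or analysis changes.

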5.6. Duration of Follow Up

Participants will be followed for 3 years after removal from study treatment or until death, whichever occurs first. Participants removed from study treatment for unacceptable adverse events will be followed until resolution or stabilization of the adverse event. Participants' vital status will be followed every 6 months following removal from the study treatment. Date and cause of death should be provided for participants who become deceased within the 3 year interval following removal from the study treatment.

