GENERAL DISORDERS AND ADMINISTRATION SITE CONDITIONS			
	Edema limbs		
Fatigue			Fatigue (Gr 3)
	Fever		
INFECTIONS AND INFESTATIONS			
	Infection ²		
INVESTIGATIONS			
	Creatinine increased		
	Lymphocyte count decreased		
	Neutrophil count decreased		
METABOLISM AND NUTRITION DISORDERS			
Anorexia			Anorexia (Gr 2)
MUSCULOSKELETAL AND CONNECTIVE TISSUE DISORDERS			
	Arthralgia		
	Back pain		
NEOPLASMS BENIGN, MALIGNANT AND UNSPECIFIED (INCL CYSTS AND POLYPS)			
		Leukemia secondary to oncology chemotherapy	
		Myelodysplastic syndrome	
NERVOUS SYSTEM DISORDERS			
	Dizziness		Dizziness (Gr 2)
	Dysgeusia		Dysgeusia (Gr 2)
	Headache		Headache (Gr 2)
RESPIRATORY, THORACIC AND MEDIASTINAL DISORDERS			

Adverse Events with Possible Relationship to Olaparib (AZD2281) (CTCAE 5.0 Term) [n= 2073]			Specific Protocol Exceptions to Expedited Reporting (SPEER)
Likely (>20%)	Less Likely (<=20%)	Rare but Serious (<3%)	
	Cough		Cough (Gr 2)
	Dyspnea		Dyspnea (Gr 2)
		Pneumonitis	

¹This table will be updated as the toxicity profile of the agent is revised. Updates will be distributed to all Principal Investigators at the time of revision. The current version can be obtained by contacting [contact]. Your name, the name of the investigator, the protocol and the agent should be included in the e-mail.

²Infection may include any of the 75 infection sites under the INFECTIONS AND INFESTATION SOC.

Adverse events reported on olaparib (AZD2281) trials, but for which there is insufficient evidence to suggest that there was a reasonable possibility that olaparib (AZD2281) caused the adverse event:

CARDIAC DISORDERS - Cardiac disorders - Other (nodal rhythm); Chest pain - cardiac; Sinus tachycardia
EAR AND LABYRINTH DISORDERS - Tinnitus
ENDOCRINE DISORDERS - Hypothyroidism
GASTROINTESTINAL DISORDERS - Ascites; Colitis; Colonic obstruction; Dry mouth; Dysphagia; Flatulence; Gastroesophageal reflux disease; Gastrointestinal disorders - Other (gastrointestinal hemorrhage); Gastrointestinal disorders - Other (intestinal obstruction); Gastrointestinal disorders - Other (intestinal perforation); Ileus; Jejunal perforation; Mucositis oral; Pancreatitis; Periodontal disease; Rectal hemorrhage; Small intestinal obstruction; Stomach pain
GENERAL DISORDERS AND ADMINISTRATION SITE CONDITIONS - Malaise; Non-cardiac chest pain
IMMUNE SYSTEM DISORDERS - Immune system disorders - Other (systemic inflammatory response syndrome)

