- **General Disorders**
The most common general AE reported was fatigue, which was observed in 52 patients (53%). Cases of fatigue were generally intermittent and of mild to moderate intensity (CTC grade 1 or 2). Other Aes included pyrexia (10 patients, 10%) and peripheral edema (16 patients, 16%).
- **Cardiac Disorders**

29 patients reported mild (CTC grade 1), asymptomatic tachycardia. None of these cases required treatment, and all events were considered to be unrelated to study drug.

- **Nervous System Disorders**

The most common nervous system Aes reported were headache (15%), dizziness (11%), and dysgeusia (13%). Other reported Aes included somnolence, attention or mental impairment, cognitive disorder, dizziness, depression, and memory impairment.

- **Hematologic Disorders**

Laboratory findings and/or clinical diagnoses of anemia (generally mild to moderate, CTC grade 1 or 2), neutropenia (predominantly mild to moderate, CTC grade 1 or 2), and thrombocytopenia (generally mild to moderate, CTC grade 1 or 2, sometimes severe) were observed. The incidence of anemia was 26%, neutropenia was 1%, and thrombocytopenia was 5%. A few cases of myelodysplasia have been reported on studies including olaparib. Additionally, data from study D0810C00002 have demonstrated increases in MCV in approximately 30% of patients, especially in those receiving greater than 6 cycles of treatment, mild and moderate in intensity, and asymptomatic in nature. No clinical consequences have been associated with this finding.

MDS/AML have been reported in <1% of patients exposed to olaparib. The cases were typical of secondary MDS/therapy-related AML. The duration of therapy with olaparib in patients who developed secondary MDS/AML varied from <6 months to >2 years. All patients had potential contributing factors for the development of MDS/AML, having received extensive previous chemotherapy with platinum agents. Many had also received other DNA damaging agents.

New primary malignancies have been reported in a small number of patients. There were other contributing factors/potential alternative explanations for the development of the new primary malignancy in all cases.

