¹ Adverse events with attribution of possible, probable, or definite that occur greater than 30 days after the last dose of treatment with an agent under a CTEP IND require reporting as follows: CTEP-AERS 24-hour notification followed by complete report within 5 calendar days for: 
 • Grade 4 and Grade 5 unexpected events CTEP-AERS 10 calendar day report: 
 • Grade 3 unexpected events with hospitalization or prolongation of hospitalization • Grade 5 expected events ² Although an CTEP-AERS 24-hour notification is not required for death clearly related to progressive disease, a full report is required as outlined in the table.									
December 15, 2004									

Note: All deaths on study require both routine and expedited reporting regardless of causality. Attribution to treatment or other cause must be provided.

- Expedited AE reporting timelines defined:
 - “24 hours; 5 calendar days” – The investigator must initially report the AE via CTEP-AERS within 24 hours of learning of the event followed by a complete CTEP-AERS report within 5 calendar days of the initial 24-hour report.

- “10 calendar days” - A complete CTEP-AERS report on the AE must be submitted within 10 calendar days of the investigator learning of the event.
- Any medical event equivalent to CTCAE grade 3, 4, or 5 that precipitates hospitalization (or prolongation of existing hospitalization) must be reported regardless of attribution and designation as expected or unexpected with the exception of any events identified as protocol-specific expedited adverse event reporting exclusions.
- Any event that results in persistent or significant disabilities/incapacities, congenital anomalies, or birth defects must be reported via CTEP-AERS if the event occurs following treatment with an agent under a CTEP IND.
- Use the NCI protocol number and the protocol-specific patient ID assigned during trial registration on all reports.

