5.10.5 Adverse Event Report Form

Purpose – Documents adverse events that occur while the participant is receiving treatment and for up to 30 days after the last dose of treatment. All adverse events are to be graded by number using the toxicity grading scale required by the protocol. This form is not for IRB submission, but for recording the AE in the research database.

Schedule for Submission – Submitted within 10 days after the last day of the cycle.

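### Non-fatal MDS/AML or new primary malignancy first arising more than 30 days after the last dose is not actively collected, and the expedited rules for such late cases conflict

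*Combined protocol and SAP*

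**What the plan says.** **Routine collection.** Section 11.1 has adverse events "collected and reported from initiation of study medication, throughout the study, and within 30 days of the last dose of study medication". Contact beyond that point is required only for events already under way. The adverse event form in Appendix G, Section 5.10.5, covers events that "occur while the participant is receiving treatment and for up to 30 days after the last dose of treatment". Section 6 words the end point differently, "through the study and until the final study visit", without saying whether that visit lies beyond 30 days. In Phase II, off-treatment assessments are due within 30 days of stopping (Section 9.2, footnote p).

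**Follow-up.** Section 5.6 keeps patients under follow-up for 3 years or until death. Its stated content is that "vital status will be followed every 6 months", plus date and cause for those who die.

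**The risk.** The olaparib table in Section 6.1.1 lists "Leukemia secondary to oncology chemotherapy" and myelodysplastic syndrome in its rare-but-serious column. Both rows are blank in the column of exceptions to expedited reporting (SPEER). Section 6.1.2 gives MDS/AML in under 1% of exposed patients, notes extensive earlier platinum treatment in the cases, and mentions new primary malignancies in a small number of patients.

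**Late reporting.** Section 11.1 adds: "Participants should be instructed to report any serious post-study event(s) that might reasonably be related to participation in this study". For related events beyond 30 days, the Phase 2 and 3 footnote in Section 11.5.1 puts "Grade 4 and Grade 5 unexpected events" on the 24-hour track. It adds unexpected Grade 3 events with hospitalization and expected Grade 5 events on a 10-day track. The Phase 1 footnote likewise names Grade 4 only when unexpected, and Grade 5 in either case.

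**The concern.** The protocol names a serious delayed risk for one of its drugs, keeps patients under follow-up for 3 years, and specifies nothing in that follow-up that would find the event. Phase II admits patients with any number of platinum lines in the recurrent setting (Section 3.1.3), the background that Section 6.1.2 associates with the reported cases.

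A patient who develops MDS three months after stopping and later dies of ovarian cancer could leave no trace in the adverse event data, because the recorded cause of death would be ovarian cancer. A count of zero in the toxicity table could then mean that no case occurred or that nobody asked after day 30. Toxicity is a secondary endpoint of Phase I and Phase I-T (Section 14.1.5). It is not a listed Phase II endpoint, but Section 14.3.1 makes all patients evaluable for toxicity from first treatment and sets no end date.

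**Working it through.** The plan states no figure on this point, so there is none to reproduce. The check is mainly of the text, with a small calculation for scale.

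**Step 1. Which cases are at issue?**
- On treatment or within 30 days of the last dose: collected routinely (Section 11.1; Appendix G, 5.10.5).
- Fatal, related, after 30 days: reportable whether expected or not (both footnotes in Section 11.5.1). Cause of death is also recorded (Section 5.6).
- Non-fatal, first arising after 30 days: no routine form, and no follow-up item stated in the documents. This is the gap.

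**Step 2. Do the expedited rules close it?**

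| Place | Time limit | Depends on expectedness? |
|---|---|---|
| 11.5.1, footnotes | applies after 30 days | Yes: non-fatal Grade 3 (hospitalized) and Grade 4 only if unexpected |
| 11.5.1, hospitalization bullet (Grades 3 to 5) | none stated | No, apart from listed exclusions |
| Appendix G, 7.2 (all Grade 4 and 5) | none stated | No |
| 11.1, participant self-report | after study | No, but relies on the patient |
| 11.1, investigator notice to IRB and regulators | after study | Worded for unanticipated events |

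The first row conflicts with the second and third. If the hospitalization bullet applied after 30 days, the footnotes' separate line for unexpected Grade 3 events with hospitalization would be largely redundant. Appendix G, 7.2, opens by deferring to Section 11, where the narrower footnotes stand.

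**Step 3. Is MDS/AML expected?** Section 11.2.3 treats an event on the adverse event list as expected and points to Section 6.1, where both terms appear. Section 6.1.1 says that, for expedited reporting, the expected events are those in a subset it calls ASAEL. The tables print SPEER in its place, and neither term is on it. The first reading makes a late Grade 4 case expected and outside the footnotes; the second makes it unexpected and inside them.

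**Step 4. Scale.** Inputs: N = 148, the planned maximum (Section 1.1), all on olaparib-containing treatment; 45 per Phase II arm (Section 14.2); rate p below 1% (Section 6.1.2). The documents give no closer value, so p = 0.2%, 0.5% and 1% are assumptions, with 1% as the ceiling.

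Expected cases = N × p. Probability of at least one = 1 − (1 − p)^N.

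| p | 148 × p | P(at least one) |
|---|---|---|
| 0.2% | 0.30 | 0.256 |
| 0.5% | 0.74 | 0.524 |
| 1% | 1.48 | 0.774 |

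These are cases at any time. If a share s first arises after 30 days, expected late cases are 148 × p × s. The documents do not give s, so the range runs from 0 (s = 0) to 1.48 (p = 1%, s = 1); p = 0.5% with s = 0.5 gives 148 × 0.005 × 0.5 = 0.37.

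One uncollected case is 1/45 = 2.2% of a Phase II arm, or 1/148 = 0.7% overall.

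**The case against.** The strongest reply is that several routes could bring a late case in. Appendix G, 7.2, asks for all Grade 4 and 5 toxicities without a time limit. The hospitalization bullet in Section 11.5.1 has none either, and a neighbouring bullet covers lasting disability after treatment. Patients are told to report serious related events. On the Section 6.1.1 reading, MDS/AML is not expected at all, so even the narrow footnotes would require a Grade 4 report.

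Much of this stands. A reader might infer that late MDS/AML lies outside both routine and expedited reporting and is required nowhere. The documents do not support that. The routes exist; they conflict with the footnotes or are passive, and an expedited clock starts only when the investigator learns of the event. An outpatient diagnosis at another hospital need not reach the site.

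Three other inferences also fail:
- The statement that "The duration of therapy with olaparib in patients who developed secondary MDS/AML varied from <6 months to >2 years" describes time on drug. It says nothing about onset after stopping.
- The documents do not grade MDS/AML, so calling a late case Grade 4 is an assumption.
- Section 5.6 does not say that each patient is contacted every 6 months. Section 12.1.2 does tie the Follow up/Survival form to a visit date or call, so contact is contemplated. The form's fields are not in the documents, and Appendix G, 5.10.8, says only that it summarizes status.

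It is also fair that no primary or efficacy result is affected.

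**Conclusion.** The point holds as an ascertainment gap limited to non-fatal MDS/AML or new primary malignancy first arising more than 30 days after the last dose. For these, no passage provides active collection, and the expedited rules give different answers depending on which is read. Cases on treatment, cases within 30 days and related deaths are covered.

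The expected number is small: at most about 1.5 MDS/AML cases among 148 patients at the 1% ceiling, with an unknown fraction arising late. That rests on the assumed 0.2% to 1% range and on full enrollment. The case for acting is that a zero count for a listed serious risk would be hard to interpret, and that correcting this costs little. It is a worthwhile improvement and does not threaten the trial's main conclusion.

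**What to change.** 1. In Sections 5.6 and 11.1, add MDS/AML and new primary malignancy (yes/no, date, type) to the existing Follow up / Survival form at the 6-monthly follow-up, for all treated patients.
2. In Section 14.3.1, state that these events are tabulated at any time after first dose, whether or not they are classed as expected, with those first arising after 30 days shown separately.
3. Reconcile the late-reporting passages (the footnotes and the hospitalization bullet in Section 11.5.1, and Appendix G, 7.2), the two accounts of expected (Sections 11.2.3 and 6.1.1), and the two end points for collection (Sections 6 and 11.1). Which reporting rule should prevail is for the sponsor to decide.

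The cost is a few form items and one short amendment. The downside is that later events are harder to attribute to study drug, since patients may have had further treatment; recording dates and type helps a reader judge this but does not remove the difficulty.
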